The patient-level effectiveness outcome and primary outcome for our project will be whether or not women get "screened" during the project. There are three ways a woman can be considered "screened." The first is to return their HPV self-test and test negative for high-risk HPV types. The second is to return their HPV self-test, test positive for high-risk HPV types, and then attend a follow-up appointment at their health system. We are requiring these women to attend a follow-up appointment to be considered "screened" given their HPV infection. The third way is to receive a clinic-based screening test (e.g., Pap test), regardless of HPV self-test return status. This will most likely apply to women in Group 2 health systems during the Usual Care Continued phase, but past studies have shown that some women will get a Pap test after receiving an HPV self-test in the mail (without using the self-test).⁴² All women not meeting one of these three criteria will be considered "unscreened." To determine this outcome, we will examine HPV self-test return status, HPV testing results, and EHR data (follow-up appointment attendance, Pap testing, etc.) for each sampled woman.

Among women who return their HPV self-test, we will examine the timing of device return and categorize each as returned within two weeks of distribution (i.e., prior to any PN) or after two weeks of distribution (i.e., following PN). We will also examine HPV testing results (positive or negative for high-risk HPV types) and collect data from EHR on the number of normal and abnormal clinic-based cervical cancer screening tests received by each woman and any cervical abnormalities found (i.e., low-grade squamous intraepithelial lesion, etc.).

To assess if the intervention is equitable (Figure 4), we will examine patient characteristics via data from HER (e.g., age and when their most recent clinic-based cervical cancer screening test prior to project entry occurred [if

ever]). Lastly, to assess safety, we will examine data from the patient satisfaction survey to see if women report any issues about using their HPV self-test. We do not anticipate such reports to be common, as HPV self-test devices have been used safely and easily by women in several research studies.⁶⁻¹⁵

Sample Size

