The project's total sample size will be 1800 women across Years 2-5 (900 women from Group 1 clinics/health systems and 900 from Group 2 clinics/health systems). These sample sizes are feasible given the expected sampling frame size (see Table 1) and will give us at least 90% power for the below analyses.⁴³ The power calculation assumed a two-sided alpha=0.05, an intraclass correlation coefficient<0.017 (based on our pilot study), and the below outcome occurrences.

Primary Analyses

Primary analyses will examine the proportion of women from Year 2 screened, as defined above, and use an intent-to-treat approach. To compare treatment groups (Group 1 vs. Group 2), we will use generalized linear mixed models (GLMMs) to account for the correlation between women from the same clinic,⁴⁴ though we expect cluster effects to be low (i.e., intraclass correlation coefficient<0.017 based on our pilot study). Since our outcome is binary, we will use a logit link to estimate odds ratios for the GLMMs. We expect that 30% of women from Group 1 clinics/health systems and 10% of women in Group 2 clinics/health systems will be categorized as screened. The primary model will be unadjusted, but we will conduct sensitivity analysis that include potential confounders due to imbalance from randomization ($p<0.10$ when comparing groups). Results will determine the effectiveness of the intervention in increasing cervical cancer screening compared to usual care.

Secondary Analyses

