We will conduct several secondary analyses for Aim 1. First, we will examine the proportion of HPV self-test returners who returned their self-test following receipt of PN. Results will provide valuable data on the added benefit of PN on HPV self-test return. Second, we will use GLMMs with a logit link to examine potential differences in the proportion of women screened across project years within each treatment group (i.e., comparing Years 2, 3, 4, and 5 for Group 1). Results will determine how screening rates changed over time, which will be key in assessing whether the intervention was maintained during the Bundling and Sustainability phases. Third, to assess if the intervention was equitable, we will use GLMMs with a logit link to examine if patient characteristics are associated with women being categorized as "screened". Fourth, to assess safety, we will descriptively examine women's reports of any issues experienced when using their HPV self-test. Lastly, we will descriptively examine the prevalence of high-risk HPV infection, abnormal clinic-based cervical cancer screening tests, and cervical abnormalities among women.

Aim 2 (Implementation Outcomes)

Implementation outcomes will examine the fidelity, sustainability, and cost-effectiveness of the intervention. We hypothesize that the intervention will be implemented with high fidelity and sustained by the clinics/health systems (Hypothesis 2a). We also hypothesize that the intervention will be a cost-effective strategy for increasing cervical cancer screening (Hypothesis 2b).

Fidelity

We will use several strategies to ensure and examine fidelity (i.e., the degree to which the intervention is conducted according to protocol). At the patient-level, we will develop an electronic tracking system to track all mailings (e.g., self-test distribution) and other data collection activities. At the provider level, we will conduct the provider education sessions using a standardized PowerPoint presentation. Data during the sessions will be collected using a checklist (for project team use only) that includes key observations related to fidelity (e.g. the presence of participants during entire session).

Sustainability

We will examine the screening rates during the Sustainability phase(s) for both Groups 1 and 2 to determine sustainability.

Cost-effectiveness

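### Maintenance and sustainability are assessed only on the overall screened rate, so a partial decline in kit-based screening is diluted and one offset by more clinic testing can be missed

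*Combined protocol and SAP*

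**What the plan says.** All references are to the combined protocol and SAP, under Statistical Methods unless stated otherwise.

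- **Aim 1, Measures** defines three routes to being screened: kit returned and negative; kit returned, positive and follow-up attended; or a clinic test. On the last it says: "The third way is to receive a clinic-based screening test (e.g., Pap test), regardless of HPV self-test return status". The same section says that return status, HPV result and health-record data are examined for every sampled woman.
- **Aim 1, Primary Analyses** gives the expected Year 2 rates: "We expect that 30% of women from Group 1 clinics/health systems and 10% of women in Group 2 clinics/health systems".
- **Aim 1, Secondary Analyses** compares the proportion screened across project years within each group in a logit mixed model, "which will be key in assessing whether the intervention was maintained during the Bundling and Sustainability phases".
- **Aim 2, Sustainability** is one sentence: "We will examine the screening rates during the Sustainability phase(s) for both Groups 1 and 2 to determine sustainability". It gives no criterion and no breakdown by route.
- **The only planned kit-return analysis** (Aim 1, Secondary Analyses) is the share of returners who returned after navigation. Its denominator is returners, and it is not described by year.
- **Randomized trial activities, Years 2 to 5:** 600 women are sampled per group in Year 2, then 100 per group in each later year. Group 2 receives no kits in Year 2. Both groups receive kits from Year 3.

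**The concern.** In Year 2 the overall outcome causes no difficulty. Group 2 shows how much screening occurs without a kit, and the comparison removes it. After Year 2 that reference is gone. A year-on-year change in the overall rate then mixes two things: a change in what the kit programme delivers, and a change in clinic testing.

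Hypothesis 2a says that clinics and health systems will sustain the intervention, and the Sustainability phase tests whether they can run kit mailing and navigation themselves. A rate that includes clinic tests does not identify that activity. If kit use weakened while clinic testing rose, the overall rate could look maintained. If clinic testing fell, a well-run kit programme could look as if it were failing. The returners-only navigation analysis would not help, because it can stay constant while the number of returned kits drops.

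**Working it through.** **1. The plan's own figure.** Sample Size says the samples "will give us at least 90% power for the below analyses". Inputs: "The power calculation assumed a two-sided alpha=0.05"; "an intraclass correlation coefficient<0.017 (based on our pilot study"); 30% against 10%; 600 women per group; five health systems per group.

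- Women per system: 600/5 = 120. Design effect: 1 + (120 − 1) × 0.017 = 3.023. Effective n: 600/3.023 = 198.5 per group.
- Power is 99.9%, or 99.4% with a t reference on 8 degrees of freedom.

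The claim holds for the primary comparison. It cannot be checked for the year-on-year comparisons, because no later-year rates are given.

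**2. Splitting the 30%.** The plan gives no background rate for women who are sent kits. The nearest figure is Group 2 in Year 2: "10% of women in Group 2 clinics/health systems will be categorized as screened". Taking 10 points as background leaves 30 − 10 = 20 points through the kit (additive split). The 5% expected after the reminder letter is used as the lower value, and 15% is an assumed upper value.

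**3. Dilution.** If kit-based screening halves and background is stable:

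| Background | Overall rate | Relative fall | Kit-based rate | Relative fall |
|---|---|---|---|---|
| 5% | 30% → 17.5% | 42% | 25% → 12.5% | 50% |
| 10% | 30% → 20% | 33% | 20% → 10% | 50% |
| 15% | 30% → 22.5% | 25% | 15% → 7.5% | 50% |

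At 10% background the absolute change is 10 points on either outcome. On the planned logit scale the odds ratios differ: (0.20/0.80)/(0.30/0.70) = 0.58 overall, and (0.10/0.90)/(0.20/0.80) = 0.44 for the kit.

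**4. Power, Group 1, Year 2 (600) against one later year (100), no clustering.** Power = Φ[(|p1 − p2| − 1.96 × SE0)/SE1], where SE0 uses the pooled proportion and SE1 the two separate ones.

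- Overall, 30% against 20%: pooled 0.2857, SE0 0.0488, SE1 0.0442. (0.10 − 1.96 × 0.0488)/0.0442 ≈ 0.10, so power is 54%.
- Kit-based, 20% against 10%: pooled 0.1857, SE0 0.0420, SE1 0.0342. (0.10 − 1.96 × 0.0420)/0.0342 ≈ 0.52, so power is 70%.

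A simulated Wald test from a logistic model gives the same 54% and 70%. An unpooled normal approximation gives 62% and 83%, which is too favourable for the planned model.

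| Scenario (kit-based screening halves) | Overall | Kit-based |
|---|---|---|
| Group 1, 5% background | 76% | 83% |
| Group 1, 10% background | 54% | 70% |
| Group 1, 15% background | 32% | 52% |
| Group 1, 10%, clustered | 38% | 50% |
| Group 1, 10%, Years 4 and 5 combined (200 women) | 80% | 93% |
| Group 2, 10%, Year 3 against Year 5 (100 against 100) | 37% | 51% |
| Group 2, 10%, clustered | 29% | 40% |

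The clustered rows use a design effect of 3.023 in Year 2 and 1 + (20 − 1) × 0.017 = 1.323 in a later year. They are conservative, because the same systems recur.

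**5. Offsetting.** If kit-based screening falls from 20% to 10% and clinic testing rises from 10% to 15%, the overall rate goes from 30% to 25%. Power on it is 16% in Group 1 and 12% in Group 2, against 70% and 51% on the kit-based outcome. To hold the overall rate at 30%, clinic testing would have to reach 20%.

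**6. Full collapse.** If kit-based screening stops and background stays at 10%, the overall rate goes from 30% to 10%. Power is over 99% in Group 1 (97% clustered) and 95% in Group 2 (88% clustered). Hiding this would need clinic testing to triple, from 10% to 30%.

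**The case against.** The strongest reply is that screening is the declared primary outcome and the unit of the cost-effectiveness ratio, so judging maintenance on it is coherent. That stands, and it is why the overall outcome should stay in the analysis. Other parts of the reply also stand:

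- **Stable background cancels.** The planned comparison is between years within a group, so a constant background drops out of the absolute difference. Bias arises only if clinic testing drifts. Otherwise the cost is precision and a weaker odds ratio.
- **Clinic tests may be prompted by the intervention.** A reader might infer that every clinic test is unrelated to the kit. Aim 1, Measures says otherwise: past studies show that some women have a Pap test after being mailed a kit they do not use. Provider education and navigation could also prompt a clinic visit. A kit-only outcome would miss these tests, and would count a move from kits to clinic tests as failure.
- **The 10% is not a clean background.** It is Group 2's expected rate after an additional reminder letter and an information sheet. At 5% the gain from the kit outcome is small (76% to 83%).
- **Sample size is the larger limit.** With 100 women per group-year, power is modest on either outcome.
- **The component data exist**, so a breakdown by route would remain possible without a prespecified analysis.

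The reply does not supply a planned analysis that separates programme performance from clinic testing after Year 2. The data allow one, but the plan does not commit to it or say how it would bear on the maintenance conclusion.

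**Conclusion.** The point holds for partial decline and for decline offset by clinic testing. Both maintenance assessments rest on the overall rate alone, no usual-care group remains from Year 3, and no kit-based rate per woman sampled is planned by year or phase. In Group 1 without clustering, power to detect a halving of kit-based screening is about 54% on the overall rate against 70% on the kit outcome, with ranges of 32–76% and 52–83% over backgrounds of 15% to 5%. A 5-point rise in clinic testing cuts the overall figure to about 16%. These figures rest on an additive split of the expected 30% that the documents do not give.

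A reader might go further and infer that a collapse of the kit programme could pass unnoticed. The plan's own rates do not support that: a fall from 30% to 10% would be detected with high power. Nor do the documents support replacing the overall outcome, since that would discard the primary outcome and any clinic testing that the intervention prompts. The case is for adding a second outcome.

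**What to change.** In Aim 1, Secondary Analyses (the comparison across years) and Aim 2, Sustainability:

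1. Keep overall screened in the year-by-year model and the Sustainability analysis.
2. Add screened through the kit (returned and negative, or returned, positive and followed up) as a second outcome in the same mixed model, with all women sampled that year as denominator. Women complete an eligibility form from Year 4, so state how those who do not return it are counted.
3. Report kit return and the clinic route alone, by year and phase, beside these.
4. Base the statement that the kit programme was maintained on both outcomes, and say in advance how they will be read together.
5. For Group 2, make the maintenance comparison over Years 3 to 5, since no kits are sent in Year 2.

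The cost is SAP wording and one extra model on data already collected, with no added women or procedures. Two limits remain and should be stated: the kit-based outcome omits clinic tests prompted by the intervention, and 100 women per group-year still restricts power.

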Cost-effectiveness analyses will be conducted from a payer perspective. We will first conduct a cost identification analysis. We will carefully consider all costs of the intervention, including those for HPV self-test devices, PN training/implementation, staff, mailing costs, and administrative costs. We will value the costs of each item using standard costs, and we will carefully distinguish costs related to scientific research from those of the interventions themselves. We will only include the intervention costs in our cost-effectiveness analyses. We will then aggregate the measures of costs and intervention effectiveness and calculate incremental cost-effectiveness ratios (ICER). The ICER measures the cost at which an added unit of outcome can be achieved by the intervention. Thus, the ICER will represent the marginal cost of an additional patient screened for cervical cancer due to the intervention. We will also conduct sensitivity analyses.

Aim 3 (Client Outcomes)

For client outcomes, we will determine the satisfaction with the multilevel intervention at the patient- and provider-levels (Table 2).

Table 2. Client Outcomes and Data Sources

Outcome	Measure	Level	Data Source
Satisfaction	Satisfaction with HPV self-testing and PN	Patient-level	Patient satisfaction survey
Satisfaction	Satisfaction with provider education sessions and change in knowledge, attitudes, and beliefs	Provider-level	Surveys from provider education sessions

Patient-Level

We hypothesize that women will report high levels of satisfaction with HPV self-testing (if HPV self-test is returned) and PN (if received) (Hypothesis 3a). Patient-level satisfaction data will come from the patient satisfaction surveys sent to women. We will examine satisfaction with both the HPV self-test device (appearance, usability, return process, etc.) and its instructions (appearance, readability, etc.). We will use items based on those from our pilot study to assess these constructs.²⁴ For women who received PN, we will also assess their satisfaction with PN using items from our past PN research.³⁴ All satisfaction items will use 5-point Likert response scales. We will consider means of 4.0 and greater to indicate high levels of satisfaction. We expect about 80% of women who were sent an HPV self-test to return a completed patient satisfaction survey (based on mailed survey return in our pilot study²⁴).

Provider-Level

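### The cost-effectiveness ratio is declared from a payer perspective, but its cost rule admits only intervention costs, so as written it is a programme cost per additional woman screened

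*Combined protocol and SAP*

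**What the plan says.** All of the costing rules stand in one paragraph, Cost-effectiveness under Aim 2 (Implementation Outcomes):

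- Perspective: "Cost-effectiveness analyses will be conducted from a payer perspective".
- Cost identification: "We will carefully consider all costs of the intervention, including those for HPV self-test devices, PN training/implementation, staff, mailing costs, and administrative costs".
- Separation from research: "we will carefully distinguish costs related to scientific research from those of the interventions themselves".
- Restriction: "We will only include the intervention costs in our cost-effectiveness analyses".
- The ratio: "the ICER will represent the marginal cost of an additional patient screened for cervical cancer due to the intervention".
- Robustness: "We will also conduct sensitivity analyses", with no content given.

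Three other places bear on how this reads. The end of Section 1 lists the components of the intervention: mailed self-testing, provider education sessions and patient navigation. Measures, under Aim 1, gives three routes to being screened: a negative self-test; a positive self-test where the woman must "then attend a follow-up appointment at their health system"; or a clinic-based test, whatever happened to the self-test. The Year 2 Medical Record Review collects clinic-based tests in both groups, and follow-up attendance for Group 1 women with a positive self-test.

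**The concern.** The effect in the ratio is the difference in women screened. Two of the three routes to that status need a clinic service: the follow-up appointment after a positive self-test, and the clinic-based test. In Year 2 the clinic-based test is the only route open to Group 2, because no self-tests are sent there. Neither service is a listed component of the intervention, and nowhere do the documents say that either will be costed.

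Under the restriction, the women screened in Group 2 carry no cost for the tests that screened them. An HPV-positive woman in Group 1 counts as an effect only once she attends a visit whose cost is not counted. A payer's incremental cost would include the difference between the arms in both services.

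Hypothesis 2b, that the intervention is cost-effective, rests on this ratio. If the cost boundary is left open, two analysts could follow the same paragraph and report different ratios, and the choice could be made after the results are known.

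**Working it through.** The documents give no unit cost, ratio or cost-effectiveness threshold, so there is no stated figure to reproduce. What can be checked is how sensitive the ratio is to the omitted items. I use Year 2, the only year with a usual-care group.

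**Inputs from the documents.** Expected proportions screened are 30% in Group 1 and 10% in Group 2 (Primary Analyses), with 600 women sampled per group in Year 2.

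**Step 1: the multiplier.** The effect per woman is 0.30 − 0.10 = 0.20, or 600 × 0.20 = 120 additional women screened. The ratio is incremental cost per woman divided by 0.20. Each $1 per woman of omitted net cost therefore moves it by 1/0.20 = $5. This step needs no outside figure.

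**Step 2: the form of the shift.** Let q be the share of Group 1 women with a clinic-based test, v the share with a follow-up visit after a positive self-test, C the clinic-test price and F the follow-up price. The Group 2 clinic-test share is 0.10. Then

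shift = [(q − 0.10) × C + v × F] / 0.20.

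The clinic-test term is negative if q is below 10%, zero at 10% and positive above it. For example:

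| q | clinic-test term |
|---|---|
| 0% | −0.50 × C |
| 5% | −0.25 × C |
| 10% | 0 |
| 15% | +0.25 × C |

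The follow-up term can only raise the ratio: +0.15 × F at v = 3% and +0.30 × F at v = 6%.

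**Step 3: an illustration on assumed inputs.** None of these is in the documents:

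- HPV positive among returned self-tests, p: 15–25%
- attendance at follow-up, f: 60–90%
- Group 1 women screened by clinic test only, q: 3–8%
- C: $100–200
- F: $200–600

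The return rate r is set so that Group 1 reaches its expected 30%:

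r = (0.30 − q) / [1 − p(1 − f)], and v = r × p × f.

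- Lowest shift (p = 15%, f = 60%, q = 3%, C = $200, F = $200): r = 0.27/0.94 = 0.2872 and v = 0.02585. Shift = [−0.07 × 200 + 0.02585 × 200]/0.20 = (−14.00 + 5.17)/0.20 = **−$44**.
- Highest shift (p = 25%, f = 90%, q = 3%, C = $100, F = $600): r = 0.27/0.975 = 0.2769 and v = 0.06231. Shift = [−0.07 × 100 + 0.06231 × 600]/0.20 = (−7.00 + 37.38)/0.20 = **+$152**.

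**Step 4: where the sign turns.** The shift is zero when F/C = (0.10 − q)/v. At q = 3% this is 0.07/0.02585 = 2.7 for the first set of p and f, and 0.07/0.06231 = 1.1 for the second. The direction therefore depends on relative prices and on HPV positivity and attendance, which the plan does not give.

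**The case against.** The strongest reply is that the restriction completes a contrast. The sentence before it separates research costs from intervention costs, so its evident job is to keep research costs out. The list of items is also introduced as examples. Both points stand: a reader might infer that the plan expressly excludes clinic tests and follow-up visits, and it does not say so. But the list is open only within the costs of the intervention. A routine clinic test in a usual-care woman is not a cost of the intervention on any ordinary reading, so the generous reading still leaves comparator costs out.

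Three further points are fair:

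- The omission applies to both arms only for clinic-based tests, whose costs partly cancel. In Year 2 the follow-up visits that count arise in Group 1 alone.
- The documents do not identify the payer or say who pays for these visits. That they fall on the payer is inferred from the declared perspective.
- A programme cost per additional woman screened is a useful implementation measure in its own right.

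A reader might also infer that the laboratory assay is left out because it is not named. The documents do not support that. Mailed self-testing is a component of the intervention and the testing is provided free to women, so laboratory testing belongs naturally among intervention costs.

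The planned sensitivity analyses do not settle the matter, because their content is not stated.

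**Conclusion.** The point holds as a mismatch between the declared perspective and the cost rule. The exclusion is partly an inference from the wording and from the definition of the intervention. Followed as written, the rule produces a programme-cost ratio.

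The $5-per-$1 multiplier rests only on the expected 30% and 10%. The range of about −$44 to +$152 rests entirely on assumed prices, HPV positivity, attendance and clinic-only testing, and shows scale only. It is not an estimate.

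A reader might conclude that the omission flatters the intervention. That cannot be said: leaving out follow-up visits makes it look cheaper, while leaving out clinic tests makes it look dearer if self-testing replaces some of them. Nor can it be said that the verdict on Hypothesis 2b would change, since no baseline ratio or threshold is given. The primary comparison of proportions screened is untouched. The change should be made, because it is cheap and the ratio cannot otherwise be read as a payer's.

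**What to change.** Replace the restricting sentence with:

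> Research costs are excluded. Costs in each arm include intervention delivery (including HPV laboratory testing of returned self-tests), clinic-based screening tests, and the follow-up visits that count towards a woman being screened, as identified in the medical record review and valued at standard payer rates.

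Name the payer. Report the intervention-only cost per additional woman screened as a secondary figure, labelled a programme-cost ratio. A Pap test done at a follow-up visit should be costed once.

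Limiting follow-up costs to visits that count towards the outcome keeps costs and effects matched, and fits the Year 2 record review, which collects follow-up attendance only for HPV-positive Group 1 women.

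The cost is a little more analysis. The record review already gathers these events, so no new patient-level counts are needed, only unit prices. The downside is that the ratio may prove less favourable.
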